Study synopsis: **60 adults will sign consent for screening with 40 randomized** with CF and vitamin D intake less than 2000 IU daily will be randomized in a 12-week RCT to: **1**) high-dose vitamin D₃ (50,000 IU weekly plus 12 g corn-derived maltodextrin/day as the prebiotic placebo); **2**) Chicory-derived inulin (12 g/day) prebiotic plus placebo vitamin D₃; **3**) combined vitamin D₃ and inulin; and **4**) placebo vitamin D₃ and placebo prebiotic. Stool and serum will be collected at baseline and at 12 weeks in the Clinical Research Center (CRC) of the NIH-funded Georgia Clinical and Translational Science Alliance (Georgia CTSA). We will assess the feasibility of this approach and collect preliminary data on changes in gut microbiota diversity (Shannon Index as primary), composition, and richness from baseline over time using 16S rRNA gene sequencing to inform future studies. Additional measures will include high-resolution stool and plasma metabolomics.

a. Enrollment:

- Patient Selection:** We will screen for study patients from adults with CF seen for routine care at the Emory CF Center. *Inclusion Criteria:* 1) male and female patients (age > 18 years) with confirmed CF by genetic mutation and/or sweat chloride testing, 2) ~~stable pulmonary function (no greater than 5% difference in FEV1% predicted from previous measurement within the past year)~~, 3) not currently on oral or systemic antibiotics for pulmonary exacerbation 4) use of CFTR modulator therapy is allowed *Exclusion Criteria:* 1) active GI disease, abdominal pain and/or diarrhea, 2) chronic kidney disease worse than stage 3 (eGFR < ml/min per 1.73 m²), 3) any vitamin D supplement use >2,000 IU or vitamin D analogue, **(patients who are taking more than 2,000 IU of vitamin D must agree to stop the vitamin D for 6 weeks and take less than 2,000 IU of vitamin D during the study)** 4) use of immunosuppressants or history of organ transplantation, or 5) current use of probiotics or prebiotics.
- Subject identification and initial screening:** We propose to consent **60 subjects** at least to randomize **40 subjects in the following arms**. We propose to study **40 subjects (10 in each arm)** in this 2x2 factorial design study (statistical considerations below).

Patients with CF who are scheduled for routine outpatient appointments will be pre-screened for eligibility by reviewing the electronic medical record.

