8.3 Archived specimens: Study subjects may sign an additional consent form for long term storage of samples. In addition to immune function, vitamin D has been linked to several non-skeletal disease states and conditions in the general population that may be applicable to CF. One example is diabetes, a common co-morbidity in patients with CF. It is, therefore, possible that remaining specimens will be banked for future study related to vitamin D in CF but beyond the specific scope of the current study. Any stored samples will be de-identified with a specific code whose identity can only be accessed by authorized study personnel appointed by the PI. Specimens will be stored in a -80° freezer at the Vitamin D and Bone Research Laboratory at the Emory University School of Medicine Division of Endocrinology and Metabolism.

9. Participant selection

9.1 Requested sample size and expected refusal or withdrawal rate: We propose to recruit 60 subjects to sign consent in order to have 40 randomized at the study site. This is a pilot study which will provide critically needed data to adequately power a larger study. The CF Foundation funded this as a pilot and feasibility study.

9.2 Inclusion/exclusion criteria:

We will screen for study patients from adults with CF seen for routine care at the Emory CF Center.

Inclusion Criteria: 1) male and female patients (age > 18 years) with confirmed CF by genetic mutation and/or sweat chloride testing, 2) stable pulmonary function (no greater than 5% difference in FEV1% predicted from previous measurement within the past year), 3) not currently on oral or systemic antibiotics for pulmonary exacerbation, and 4) use of CFTR modulator therapy is allowed

Exclusion Criteria: 1) active GI disease, abdominal pain and/or diarrhea, 2) chronic kidney disease worse than stage 3 (eGFR < ml/min per 1.73 m²), 3) any vitamin D supplement use >2,000 IU or vitamin D analogue, 4) use of immunosuppressants or history of organ transplantation, or 5) current use of probiotics or prebiotics.

9.3 Subject recruitment plan: Recruitment will be performed through referral from the outpatient CF Clinic.

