9.4 Screening for eligibility: All patients with CF will be screened for eligibility at presentation to the CF clinic for routine visit by reviewing the subject's vitamin D intake. Screening will be completed daily by the research coordinator. Patients who have met the above inclusion criteria and have met none of the exclusion criteria on our initial assessment will be offered the opportunity to participate in our study. The study personnel will explain the study protocol in detail in the consent form as well as verbally. Any additional information regarding questions or concerns from potential or confirmed study participants will be provided by the study coordinator.

9.5 Withdrawal from study: Participants may withdraw from the study at any time. Automatic withdrawal occurs when a participant moves away from the center or refuses providing further blood, stool or sputum sample.

10. Statistical analysis

Statistical Considerations for Pilot Study:

We received this funding from the CF Foundation to test the feasibility of this 2x2 study design.

We will evaluate the feasibility of recruitment, retention, assessment and implementation of the proposed interventions. We wish to identify any potential flaws in the study design and potential challenges in the subsequent large-scale study. Our measures of feasibility will focus on metrics of recruitment, retention, acceptability & completion as adopted from the NIH/NCCIH . Our target metric of success is compared to our previous single intervention study with vitamin D (Table).

Feasibility Question	Feasibility Metric	Prior Rate	Target Metric of Success
Recruitment	Number of subjects screened a month	16.2/month	>15/month
Recruitment	Number of Enrolled/Screen Fails	1:4.05	1:4 Enrolled/Screened
Retention	Number of dropouts and reasons for dropout	13% (3 out of 23 enrolled)	<15%
Adherence	Number of subjects who adhere to assignment	Not recorded	>80%
Acceptability	Subject ratings for acceptability during and after participation	Not recorded	>3 on 5 point Likert scale
Completion	Number of subjects who complete all study procedures	73%	>70%
Completion	Duration from initiation to completion of pilot study	52 subjects in 15 months	40 randomized subjects in 15 months

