The pilot sample size of 40 randomized patients is based on the pragmatics of recruitment, patient flow, and budgetary constraints. We have preliminary data on vitamin D; however, we do not have data on prebiotics which necessitates this pilot study to adequately power a larger study.

For the vitamin D arm, our preliminary data suggest a standard deviation of 1.2 of the diversity index. In our proposed pilot study consisting of 20 subjects in each vitamin D arm, we have 29% power to detect a between-group difference of 0.5 and 56% power to detect a difference of 0.75 in the diversity index using a significance level of 0.05. For the prebiotic arm, we do not have preliminary data. However, if vitamin D and pre-biotic have a synergistic effect, there may be greater power to detect a between-group difference of 0.5 (or 0.75).

The CF Foundation acknowledges that we are underpowered as a pilot study. However, our goal is not to evaluate efficacy of the proposed interventions but to examine the feasibility of conducting this pilot in a 2x2 factorial study of a larger scale. Moreover, the pilot data from this study will give us a first impression of the variability and effect sizes of the Shannon diversity index in the patient population of interest in each of the 4 treatment arms and thus assist in the sample size and power calculation of the subsequent larger study. In addition, these pilot data will inform power calculations for our secondary outcomes. Finally, the data that we collect from this pilot will help identify modifications needed in the planning and design of the subsequent study. We will also determine between-group differences, but given that low power is characteristic of pilot studies, statistical significance is not the focus of the analysis. We will also summarize patient characteristics at baseline and during follow-up using mean \pm SD (or median and interquartile range, as appropriate) for continuous variables and frequency (percentage) for categorical variables. Statistics on the diversity index will also be reported at baseline and at 12 wks for each of the 4 treatment combinations. A qualitative review will also be provided, and this will include, among others, an evaluation of the representativeness of the subjects, a discussion on how to refine the data collection tools, how to track patients better, and how to improve implementation of the proposed interventions.

11. Adverse event reporting:

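### Section 10 quotes power for all 40 randomised (20 per vitamin D arm) with no allowance for loss after randomisation; at the earlier trial's 13% dropout, power is about 3 and 5 points lower

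*Combined protocol and SAP*

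**What the plan says.** **Sample size.** Section 5.1 (Enrollment) plans "40 subjects (10 in each arm"), so 20 against 20 for the vitamin D comparison. Section 10 says where the total comes from: "The pilot sample size of 40 randomized patients is based on the pragmatics of recruitment, patient flow, and budgetary constraints".

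**Power.** Section 10 reports that "our preliminary data suggest a standard deviation of 1.2 of the diversity index". It then gives the power at a 0.05 significance level: "In our proposed pilot study consisting of 20 subjects in each vitamin D arm, we have 29% power to detect a between-group difference". That figure is for 0.5; the plan's figure for 0.75 is 56%. It does not say whether the test is one- or two-sided, or whether the 20 are randomised or evaluable subjects.

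**Loss of subjects.** The feasibility table in Section 10 gives the earlier trial's dropout as "13% (3 out of 23 enrolled") and sets a retention target of under 15%. A separate row gives completion of all study procedures: 73% earlier, target above 70%.

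**Allowance.** Section 9.1, whose heading refers to expected refusal or withdrawal, says: "We propose to recruit 60 subjects to sign consent in order to have 40 randomized at the study site". It gives no withdrawal rate after randomisation.

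**Endpoint and analysis set.** Stool and sputum are taken only at baseline and at 3 months (Procedures to be performed; Section 8). Section 9.5 makes refusal of further samples a ground for automatic withdrawal. Section 8.2 specifies intention-to-treat. No section gives a rule for a missing 12-week sample or for replacing dropouts.

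**The concern.** The power statement treats every randomised subject as contributing to the 12-week comparison, while the same section reports earlier dropout and sets a target that accepts more of it. With only two sampling times, a subject without the second sample adds nothing to the comparison at 12 weeks. Intention-to-treat fixes the group in which a subject is counted; it does not supply the missing measurement.

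The stake is modest but concrete. Section 10 says the pilot's variability and effect sizes will be used to size a larger trial. A reader who takes the printed power at face value will expect somewhat more precision than the trial is likely to give, even if retention goes as well as it did before.

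**Working it through.** **Inputs.** SD 1.2, differences 0.5 and 0.75, alpha 0.05, 20 per arm (Section 10); earlier dropout 3/23 = 13%, dropout target under 15%, completion target above 70% (feasibility table). Assumptions: two-sided test, equal loss in both arms, and dropout taken as the share without a 12-week sample.

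**Method.** Two-sample t-test with n per arm: SE = SD × √(2/n); noncentrality = difference/SE; degrees of freedom = 2n − 2; power from the noncentral t distribution; 95% CI half-width = critical t × SE.

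**Step 1: the plan's own figure.** At n = 20, SE = 1.2 × √(2/20) = 0.379. The noncentralities are 0.5/0.379 = 1.32 and 0.75/0.379 = 1.98, and the critical t on 38 df is 2.024. Power is 25.0% and 48.7%. The normal approximation gives 26.0% and 50.7%; a one-sided t-test gives 36.3% and 61.7%. None of these is the printed 29% and 56%. The printed pair does appear with 24 per arm at SD 1.2 (29.3%, 56.4%), or with 20 per arm and an SD of about 1.095 (29.1%, 56.0%). The documents do not show that either was used.

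**Step 2: evaluable number at the earlier dropout rate.** 20 × (1 − 0.13) = 17.4 per arm.

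**Step 3: power and precision at 17.4.** SE = 1.2 × √(2/17.4) = 0.407. The noncentralities are 1.23 and 1.84, and the critical t on 32.8 df is 2.035. Power is 22.2% and 43.2%. The SE ratio is √(20/17.4) = 1.07. The half-width is 2.035 × 0.407 = 0.83, against 2.024 × 0.379 = 0.77 at n = 20.

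**Step 4: the most loss the retention target allows.** Six of 40 is exactly 15% and misses the target. Five of 40 (12.5%) meets it and leaves 35, split 18 and 17. Power is 22.3% and 43.4%, almost the same as in step 3.

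**Step 5: sensitivity and worst case.** The smallest whole number above 70% of 40 is 29, or 14.5 per arm.

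| Evaluable per arm | Power for 0.5 / 0.75, SD 1.2 | Power for 0.5 / 0.75, SD 1.095 (inferred) |
|---|---|---|
| 20 (all randomised) | 25.0% / 48.7% | 29.1% / 56.0% |
| 17.4 (earlier 13% dropout) | 22.2% / 43.2% | 25.8% / 50.0% |
| 14.5 (worst case) | 19.1% / 36.8% | 22.0% / 42.8% |

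The fall from the first row to the second is about 3 points for 0.5 and 5 to 6 points for 0.75, whichever SD is used.

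**The case against.** The strongest reply is that nothing depends on this figure. The sample size is pragmatic, Section 10 says the funder accepts that the pilot is underpowered, efficacy is not the goal, and attrition is itself one of the outcomes to be measured. Changing an admitted 25% to 22% alters neither the number randomised nor the analysis. Also, the sentence speaks of a study made up of 20 subjects per arm and never calls them evaluable, so it can be read as power conditional on full follow-up. All of this stands, and it is why the point is minor. It does not remove the point: the protocol chose to print power figures, and they should match the data it can reasonably hope to have.

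A reader might infer three stronger things that the documents do not support:

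- *That the plan expects 17 per arm.* The 15% is a ceiling for success and not a forecast, and exactly 17 per arm would miss it. The only observed rate is the earlier 13%.
- *That 14 to 15 per arm is the number the completion target implies for the endpoint.* That target covers all procedures, including sputum and dietary history. A subject who misses one of these may still return a 12-week stool sample, and the table itself separates 13% dropout from 73% completion. The two limits overlap and must not be added.
- *That every estimate of variability suffers.* Section 10 also reports the diversity index at baseline, where each subject with a baseline sample contributes.

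**Conclusion.** The concern holds as a minor reporting gap. The quoted power applies only if all 40 randomised subjects give a 12-week sample, and the plan neither says so nor allows for loss after randomisation. At the earlier dropout rate, and on the stated SD, power is about 22% and 43% where full follow-up would give 25% and 49%. The SE is about 7% larger and the CI half-width is 0.83 instead of 0.77. This rests on the assumptions listed in the working, and on a dropout rate from only 23 subjects in a single-intervention trial.

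It would go too far to say that the design cannot deliver 20 analysable per arm: loss is likely on past experience and tolerated by the targets, but it is not certain. Nor does attrition explain the mismatch between 29%/56% and the stated inputs. That is a separate discrepancy, and it runs the other way, since the printed figures are too high even at 20 per arm. The SD of 1.095 is only an inference from the printed figures.

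**What to change.** In Section 10:

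1. Reconcile 29% and 56% with SD 1.2 and 20 per arm, and state the test and its sidedness.
2. Say that 20 per vitamin D arm is the number randomised.
3. Restate power, or preferably the CI half-width, for about 17.4 evaluable per arm, citing the earlier 13% dropout. With SD 1.2 and a two-sided test this is about 22% and 43%, half-width 0.83. If step 1 shows that an SD near 1.095 was used, it is about 26% and 50%.
4. If 14 to 15 per arm is shown, label it a worst case and say that the completion target covers all procedures.

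A line on how a missing 12-week sample is handled under intention-to-treat would help, but is not essential to this point.

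The cost is a sentence or two and a slightly less favourable stated power. No extra patients are needed.

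### The stated power of 29% and 56% does not follow from the inputs printed beside it, which give about 25% and 49%

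*Combined protocol and SAP*

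**What the plan says.** The power statement is in section 10, Statistical analysis, under the considerations for the pilot study. It gives these inputs:

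- Spread: "our preliminary data suggest a standard deviation of 1.2 of the diversity index".
- Sample size: "In our proposed pilot study consisting of 20 subjects in each vitamin D arm". This agrees with section 5.1, which plans "40 subjects (10 in each arm"), so each level of the vitamin D factor has 2 × 10 = 20.
- Error rate: "using a significance level of 0.05".

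The result is "we have 29% power to detect a between-group difference of 0.5 and 56% power to detect a difference of 0.75 in the diversity index".

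The section names no test, sidedness, baseline adjustment or dropout allowance. It does not say whether 1.2 describes the index at one visit or its change, although the synopsis in section 5.1 frames the outcome as change: "collect preliminary data on changes in gut microbiota diversity (Shannon Index as primary"). It also says that the sample size "is based on the pragmatics of recruitment, patient flow, and budgetary constraints" and that the study is underpowered.

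**The concern.** The paragraph supplies everything that an ordinary two-group power calculation needs, so the two percentages should be recoverable from it. They are not. These are the only power figures in the plan, and 1.2 is its only stated measure of spread for the diversity index.

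What is at stake is mainly the label on 1.2. The pilot is meant to support the sizing of a larger study. If 1.2 is really a variance, someone who takes it forward as an SD starts from the wrong spread. If 1.2 is an SD and the comparison is unadjusted, the stated power is too high.

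**Working it through.** **Inputs (section 10).** SD σ = 1.2; n = 20 per vitamin D level; δ = 0.5 and 0.75; α = 0.05. Two-sided testing is my assumption, because sidedness is not stated.

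**Formula.** The noncentrality is λ = δ / (σ√(2/n)) with 2n − 2 = 38 degrees of freedom. Power is P(|T| > 2.024), where T is noncentral t with 38 df and noncentrality λ.

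**Attempt to reproduce the plan's figures**

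- Standard error: 1.2 × √(2/20) = 0.3795.
- δ = 0.5: λ = 0.5/0.3795 = 1.318, power 25.0% (stated 29%).
- δ = 0.75: λ = 0.75/0.3795 = 1.976, power 48.7% (stated 56%).

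**Other ways to run it on the same printed inputs**

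| Calculation | δ = 0.5 | δ = 0.75 |
|---|---|---|
| Stated in the plan | 29% | 56% |
| Two-sided t, 38 df | 25.0% | 48.7% |
| 2×2 factorial model, 36 df | 25.0% | 48.6% |
| Two-sided normal approximation | 26.1% | 50.7% |
| One-sided t | 36.3% | 61.6% |
| Two-sided t, 17 per group (15% dropout) | 21.8% | 42.4% |

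The two-sided calculations fall below both stated figures and the one-sided test lies above both.

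**Rounding of the SD.** The smallest SD that prints as 1.2 is 1.15. It gives 26.8% and 52.0% (t) or 28.0% and 54.1% (normal), still short. With n = 20 and a two-sided t-test, the SDs that round to both 29% and 56% run from about 1.089 to 1.102.

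**What would reproduce both figures.** Each line changes or adds one input. The document states none of them.

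| Change | δ = 0.5 | δ = 0.75 |
|---|---|---|
| 1.2 is a variance, SD = √1.2 = 1.095 | 29.1% | 56.0% |
| SD is 1.1 | 28.9% | 55.6% |
| 24 per arm, SD 1.2 | 29.3% | 56.3% |
| ANCOVA, assumed baseline correlation 0.41: SD = 1.2√(1 − 0.41²) = 1.095, 37 df | 29.1% | 56.0% |
| Change score, per-visit SD 1.2, assumed correlation 0.58: SD = 1.2√(2 × 0.42) = 1.100 | 28.9% | 55.6% |

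For the variance reading: the standard error is 1.095 × √0.1 = 0.3464, so λ = 0.5/0.3464 = 1.443 and 0.75/0.3464 = 2.165.

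**Illustration for a later study.** I assume 80% power, a difference of 0.5 and a two-sided 0.05 t-test. SD 1.2 needs 92 per group and SD 1.095 needs 77. The ratio is 92/77 = 1.19, about 20% more.

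**The case against.** There are three fair points on the other side.

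First, perhaps no printed number is wrong. Since the test and any adjustment are unstated, an ANCOVA or a change-score analysis with a suitable correlation would yield 29% and 56% from a per-visit SD of 1.2. This stands as a possibility, and it is why I do not say that the power is overstated. It does not rescue the text: the input that drives the result would then be missing, and the percentages still cannot be obtained from what is printed.

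Second, the variance reading is not the only candidate. A typing slip of 1.2 for 1.1 fits to the rounded percent as well, and the preliminary data are not in the document. This also stands. The variance reading is attractive because it keeps the printed number 1.2 and every other input, but it remains an inference.

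Third, the consequence is small. Nothing in the trial depends on 29% or 56%, and either pair leads to the same conclusion that the study is underpowered. The larger study is to use the pilot's own data: "the pilot data from this study will give us a first impression of the variability and effect sizes of the Shannon diversity index". If the true SD were 1.095, carrying 1.2 forward would make the later study larger rather than too small. I accept all of this. It limits the weight of the point but does not remove the inconsistency.

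**Conclusion.** The concern holds, as a minor reporting error. On the printed inputs, with an unadjusted two-sided comparison, power is about 25% and 49%. The stated 29% and 56% exceed the t-test by 4.0 and 7.3 points (29 − 25.0; 56 − 48.7) and the normal approximation by 2.9 and 5.3 points (29 − 26.1; 56 − 50.7). If 1.2 is a variance, the discrepancy in power disappears and the error is in the words standard deviation.

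Confidence is high that the figures do not agree as printed. It is not high for any one explanation, because the document does not allow a choice between them. The sample size, the feasibility criteria and the planned analyses are unaffected.

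**What to change.** Go back to the source calculation and state in section 10 whether 1.2 is an SD or a variance, whether it refers to one visit or to the change from baseline, and which test, sidedness and adjustment were used. Then:

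- If 1.2 is an SD and the test is an unadjusted two-sided t-test with 20 per arm, restate the power as about 25% (0.5) and 49% (0.75).
- If 1.2 is a variance, or the SD should read 1.1, print the SD as about 1.1 and keep 29% and 56%.
- If another n per arm or a baseline adjustment was used, state that n or the assumed correlation beside the percentages.

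The percentages should not be replaced before the source is checked, since they may be the correct part. The cost is one or two sentences, with no added patients, procedures or analyses.

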Vitamin D dose: We have conducted a number of studies demonstrating very effective use of vitamin D₃ at a dose of 50,000 IU weekly in the adult CF population. Our study in 2009 demonstrated that vitamin D₃ was superior to vitamin D₂ or UV lamp therapy in CF⁴³. Subjects receiving weekly doses of oral vitamin D₃ 50,000 IU for 12 weeks raised mean serum 25(OH)D concentrations from 21 ± 10 to 47 ± 20 ng/mL ($p < 0.001$) with 100% of subjects achieving a serum 25(OH)D greater than 30 ng/mL. We conducted a more recent study examining our dosing regimen of vitamin D3 50,000 IU vs placebo weekly for 12 weeks on gut microbiota in patients with CF and found that serum 25(OH)D increased significantly in the vitamin D₃ group from a mean of 24.99 ± 5.05 to 45.29 ± 21.01 ($p < 0.05$) compared to no change in placebo. Therefore, for this study we will use our established vitamin D dosing regimen of vitamin D₃ 50,000 IU once weekly for 12 weeks. As in past studies, we will obtain the vitamin D₃ and matching placebo capsules from Bio-Tech Pharmacal, Inc.

Inulin: Inulin is non-digestible fiber found in many food products. Inulin is also available as an over the counter supplement. Inulin will be provided from the brand name "Now Foods". This is a commercially available inulin supplement that is available in powder form. We have been in contact with the investigational pharmacy who will make sachets of 12 grams of Jetsu inulin for the active inulin group and 12 grams of

maltodextrin which is a food additive and commonly used as a control to inulin. Subjects will be asked to dissolve a sachet daily into a beverage of their choice (coffee, tea, water) and to ingest this daily.

All study drugs will be dispensed by the Investigational Drug Pharmacy.

- 6. Follow-up studies:** Patients will be followed throughout the duration of the study for 3 months. Subjects will provide their stool and sputum sample either in person or return by mail. For those subjects seen in person, participants will be seen for study follow-up visits at 3 months (+/- 4 weeks) as scheduled for their usual medical care (routine outpatient follow-up visits). Interim phone calls will be made to participants on a bi-weekly basis after week 1 to remind about taking pills. This will be done by the co-investigator. At the end of 3 months, we will obtain repeat stool and sputum samples from the entire cohort.

Procedures to be performed:

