All adverse events will be documented and reviewed by the PI. These will be enumerated and reported according to IRB policies. Any serious adverse events will be reported within 24 hours to the IRB. They will be reviewed by all investigators and a disposition determined before proceeding with further enrollment.

12. Data and safety monitoring plan (DSMP)

The procedures associated with this research trial are associated with minimal risk. Therefore, no formal data safety monitoring board will be appointed. Our data safety and monitoring plan will be as follows: The physical risks associated with this study are associated with venipuncture, any adverse events associated with venipuncture will be monitored by the site study coordinator and reported to the study PI, [name]. Adverse events will then be reported to the Emory IRB within the timeframe stipulated by IRB regulations.

Oversight of the progress and safety of the trial will be provided by the PI. Adverse events are not anticipated, but any occurring will be documented and reported according to Emory IRB policies and procedures. Cumulative adverse events and study progress summary will be communicated to the IRB at the time of continuing review.

Anticipated Adverse Events:

Untreated vitamin D deficiency: Subjects enrolled in the placebo arm of this study may have 25(OH)D less than 30 ng/mL which is considered vitamin D insufficient by the present CFF guidelines. Vitamin D deficiency does not generally result in clinical symptoms. The study will be completed over the course of 3 months and thus long term consequences of low vitamin D would be unlikely. There is currently no evidence that short duration (3 month) period of not receiving supplemental vitamin D affects morbidity and mortality in CF. Moreover, at the end of the 3 months, both groups will be treated with 1000 IU Vitamin D daily to ensure that the group that did not get vitamin D will be treated.

Vitamin D Toxicity/Hypercalcemia: One of the potential risks of taking high amounts of vitamin D is vitamin D toxicity. This would manifest as hypercalcemia. The risk of this will be minimal since the dose of vitamin D that has been proposed in the intervention arm is 50,000 IU once a week for 3 months which has been recommended by the CF foundation as standard of care for treatment of vitamin D deficiency.

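### The safety plan names hypercalcemia but plans no targeted check for it, and its minimal-risk argument omits permitted background vitamin D and participants who are not deficient

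*Combined protocol and SAP*

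**What the plan says.** **Monitoring.** The DSMP (section 12) opens on blood sampling: "The physical risks associated with this study are associated with venipuncture, any adverse events associated with venipuncture will be monitored by the site study coordinator". It has the coordinator report these events to the principal investigator. It continues: "Adverse events are not anticipated, but any occurring will be documented and reported". A list headed as anticipated adverse events follows, covering untreated deficiency, vitamin D toxicity and discomfort from inulin. Section 11 is broader: "All adverse events will be documented and reviewed by the PI". Section 12 also gives patient monitoring to the principal investigator and co-investigators. Section 7 (Risk/benefits) uses the biweekly adherence calls to ask about the gastrointestinal effects of inulin.

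**Hypercalcemia.** On vitamin D toxicity the DSMP says: "This would manifest as hypercalcemia. The risk of this will be minimal since the dose of vitamin D that has been proposed". The reason given is that 50,000 IU once a week for three months is the CF Foundation's recommended treatment for vitamin D deficiency.

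**Background vitamin D.** The synopsis in section 5.1 describes participants with an intake below 2,000 IU daily. The exclusion criteria there require people on higher doses to stop for six weeks and then to "take less than 2,000 IU of vitamin D during the study". Section 8.2 says the medical record is flagged to prevent vitamin D use.

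**Blood.** The synopsis says: "Stool and serum will be collected at baseline and at 12 weeks". Section 8.1, the procedures list and the data collection chart name only stool and sputum.

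**The concern.** Each of the two products has a side effect named in the plan. The inulin effects are actively asked about; the vitamin D toxicity is not. No section provides for a calcium measurement, a 25(OH)D safety measurement or a symptom question aimed at hypercalcemia. The one risk given an explicit coordinator-to-investigator chain belongs to a procedure that the specimen section does not list.

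The argument that the risk is minimal concerns one dose in one population. The plan's own rules admit a larger total intake and a wider population.

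If nothing changes, hypercalcemia would come to light only if a participant reported symptoms or routine care happened to find it. A report of no cases would then say little, and the larger study that this pilot is meant to prepare could carry forward a risk statement that does not describe the intake or the people allowed.

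**Working it through.** **1. Intake behind the risk statement, against intake allowed**

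Inputs: assigned dose 50,000 IU weekly (sections 5.1 and 12); background vitamin D below 2,000 IU (section 5.1). The exclusion criterion gives no time unit. Per day is assumed, because the synopsis says daily.

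Total weekly intake = 50,000 + 7 × daily background intake.

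| Background (IU/day) | Total (IU/week) | Ratio to 50,000 |
|---|---|---|
| 0 (basis of the DSMP statement) | 50,000 | 1.00 |
| 500 | 53,500 | 1.07 |
| 1,000 | 57,000 | 1.14 |
| 1,500 | 60,500 | 1.21 |
| 2,000 (limit, not reached) | 64,000 | 1.28 |

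Over 12 weeks the limit is 12 × 64,000 = 768,000 IU, against 12 × 50,000 = 600,000 IU.

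**2. Population behind the risk statement, against population allowed**

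- The cited recommendation is for treating deficiency (section 12).
- Sections 3 and 4.1 describe adults with insufficient vitamin D status.
- The eligibility criteria (sections 5.1 and 9.2) contain no 25(OH)D limit, and section 9.4 screens by reviewing vitamin D intake.
- Section 12 itself says only that placebo participants may be below 30 ng/mL.

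A participant with sufficient vitamin D can therefore be randomized to the active capsule, and the deficiency argument does not cover that person.

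**3. Is background vitamin D allowed?**

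The section 5.1 criteria allow it below 2,000 IU. Section 9.2 repeats the exclusion above 2,000 IU but omits the sentence on intake during the study. Section 8.2 aims to prevent vitamin D use altogether. These statements cannot all describe the same rule.

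**4. Is blood drawn?**

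- Yes, or implied: synopsis (serum), Aim 1 (plasma metabolomics), section 9.5 (refusal of further blood), section 12 (venipuncture).
- Not listed: section 8.1, the procedures list, the data collection chart.

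Even where blood is mentioned, no calcium assay is named. Planned calcium measurements found in the document: 0.

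**5. What about 20 treated participants could show**

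Two arms of 10 receive vitamin D. If calcium were measured in all 20 and no case were found, the one-sided 95% upper limit for the risk would be 1 − 0.05^(1/20) = 0.139, or about 14%.

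**The case against.** The plan does not ignore adverse events. A reader might infer from the DSMP's opening that only venipuncture events are monitored. The documents do not support that: section 11 covers all adverse events and sends serious ones to the IRB within 24 hours, section 12 assigns patient monitoring to the investigators, and the calls ask about inulin effects. Symptomatic hypercalcemia could be recorded through these routes. Treating physicians are also told of participation, and medical records are reviewed. All of this stands, and it limits the gap to targeted detection.

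The 64,000 IU figure is a bound that no compliant participant reaches. The excess depends on each person's own supplements, and section 8.2 points towards none. This also stands, which is why intake can exceed the cited dose rather than does exceed it.

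A reader might also point to the earlier trial in section 5.1, where 25(OH)D went from "24.99 ± 5.05 to 45.29 ± 21.01" ng/mL, and read the rise in SD as widely varying response, or project the proportion reaching some high level. Neither step is sound. Those participants were selected for values below 30 ng/mL, which narrows the baseline SD. In the other study cited there the SD went from 10 to 20. No section ties a 25(OH)D level to hypercalcemia.

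Finally, this is a feasibility pilot that disclaims any safety claim (section 13), and 20 treated participants cannot establish that a risk is minimal. That is right. It argues for a modest remedy, not for leaving the text contradictory or a named toxicity without any check.

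**Conclusion.** The concern holds in a limited form. The DSMP names hypercalcemia, has no targeted check for it, and calls the risk minimal on grounds that fit neither the full intake nor the full population allowed. Total intake can be up to 28% above the cited dose, or 14% above at 1,000 IU a day of background vitamin D, if the 2,000 IU limit is per day and section 5.1 prevails over section 8.2. If section 8.2 prevails, the intake part falls away, but the absence of a 25(OH)D limit and of a targeted check remains. The DSMP also contradicts itself on whether adverse events are anticipated, and contradicts section 8.1 on whether blood is taken.

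The documents do not show that hypercalcemia is likely, and they give no basis for estimating its frequency. What total intake is acceptable, and for whom, is for the sponsor's clinicians.

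**What to change.** 1. Reconcile sections 5.1, 8.2, 9.2 and 12 on permitted background vitamin D, with the time unit stated. Have the sponsor's clinicians restate the risk paragraph for the intake and population actually allowed.
2. Extend the coordinator-to-investigator reporting sentence to the product risks the plan names, and delete the statement that adverse events are not anticipated. Align the venipuncture text with section 8.1.
3. Add hypercalcemia symptom questions to the existing biweekly calls, identically in all four arms so that blinding and the comparison are kept. Abstract any routine calcium result from the medical record already being reviewed, and report how many participants per arm have one. The documents do not say whether calcium is part of routine care, so coverage is unknown. Use study serum for calcium only if the sponsor confirms that the serum in the synopsis is really collected.
4. If calcium is not measured, state that the trial cannot report on asymptomatic hypercalcemia.

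Cost: a few call questions, some record abstraction, text edits, and a slightly less favourable risk statement. No new blood draw is asked for.
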